Existing studies comparing MPP and SV approaches typically report outcomes at discrete time points - post-operative day 1, week 4, month 3, and beyond²⁻⁵. These studies consistently demonstrate no significant differences in functional outcomes at 3 or 6 months and beyond post operatively²⁻⁹. They lack data, however, on recovery during the initial stages of TKA post operative recovery, a period when patients are most vulnerable to functional impairments, pain, and difficulty resuming daily activities. While a 2024 prospective study reported significantly improved early outcomes in the SV group compared to MPP at 1 and 3 months, it did not include continuous or real-time data within the first 30 days post-op, leaving this gap in our understanding of recovery during this critical period⁵.

Smart technology, including PIQ can bridge this gap by capturing continuous gait metrics, providing a view of early recovery. Prior studies using external devices (Fary et al., 2023) demonstrated the feasibility of passive gait monitoring but lacked implant-based validation. Persona IQ offers a unique opportunity to directly measure *in vivo* knee kinematics and gait parameters through the recovery period.

Study Design

This is a single-institution, prospective randomized study. Patients of [name], [name], and [name] undergoing primary total knee arthroplasty (TKA) at the Advanced Center for Joint Surgery (Sandy Springs, GA; Cumming, GA) will be screened for eligibility and approached during their pre-operative clinic visits. We plan to enroll 100-120 eligible once obtaining informed consent. For two weeks prior to surgery, enrolled patients will be asked to track their step count using the built-in iPhone Health application. If a patient routinely wears an Apple Watch or similar device, the step count data from the watch may also populate the iPhone Health application and will therefore contribute to the recorded step count. Patients will self-report their average daily step count on the day of surgery by showing the data from the application to research fellows. While recording step count, adherence will be recorded as the number of days with available iPhone Health data meeting validity criteria (≥ 500 steps). Days with 0–499 steps will not be considered valid unless the patient attests to medically-indicated low activity, in which the reason will be documented.

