- KOOS, JR. (Knee injury and Osteoarthritis Outcome Score for Joint Replacement) - Preop, 6 weeks, and 6 months
- Forgotten Joint Score - Preop, 6 weeks, 6 months

Other measures:

- Patient Demographics including
 - Age
 - Sex
 - Body Mass Index (BMI)
 - American Society of Anesthesiologists (ASA) score
- Surgical side (L/R)
- Comorbidities

ANALYSIS

Post-operative functional data will be extracted from the Canary Medical platform for all Persona IQ participants. Preoperative step count will be collected from each participant's iPhone. Descriptive and comparative statistical analyses will be conducted using this real-time data.

[figure not shown]
Data are broken down descriptively first to understand the distribution of the medial parapatellar and subvastus groups. Continuous data are presented as mean (standard deviation) and categorical data are presented as cell count (%). Shapiro-Wilks and Kolmogorov-Smirnov tests are used to assess the normality of the continuous data. T-tests are used to calculate P values for continuous data and Chi-squared tests are used to calculate P values for categorical data. Following this, an unadjusted and adjusted logistic regression are analyzed using PROMs as the dependent outcome. Significance is determined at P value < .05. All statistical analyses are done using R Studio (version 4.3.1, Vienna, Austria). Using a significance level of 5%, a power of 80% and an effect size of 0.3, we believe that 55-60 patients are needed for the MPP group and 55-60 patients are needed for the SV group to determine a difference of 1000 steps per day.

CONSENT PROCEDURE

Subjects will be identified via the surgical schedule and contacted during their pre-operative clinic visits. A research coordinator will explain the study and obtain informed consent. No study activities (e.g., device usage or data collection) will begin prior to consent. Patients may withdraw at any time.

COST AND COMPENSATION

As this is currently standard of care at Northside Hospital, no compensation will be given.

CONFIDENTIALITY OF DATA

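### An effect size of 0.3 at 5% significance and 80% power needs about 176 patients per arm, not 55–60; at that effect size the trial has about 34–37% power

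*Protocol*

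**What the plan says.** The last sentence of the statistical paragraph in the Protocol's ANALYSIS section is the only sample-size justification: "Using a significance level of 5%, a power of 80% and an effect size of 0.3, we believe that 55-60 patients are needed". This number refers to the MPP arm; the same number is described as "needed for the SV group to determine a difference of 1000 steps per day". It does not name the scale of the effect size, the SD, the sidedness of the test or any allowance for loss.

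The other elements stand elsewhere in the Protocol:

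- The INTRODUCTION names step count as the main primary outcome.
- Study Design gives each approach an equal chance of being assigned.
- ANALYSIS compares continuous data by t-test and sets the threshold: "Significance is determined at P value < .05".
- Study Design gives the recruitment target: "We plan to enroll 100-120 eligible once obtaining informed consent", which is 50–60 per arm.

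**The concern.** The sentence links an effect size, a significance level and a power to a number of patients, so it can be checked directly. A standardised difference of 0.3 is a small-to-moderate effect, and 55–60 per arm is far too few to detect it with 80% power in a two-group comparison of means.

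If the true difference is 0.3 SD, the trial would miss it about two times in three. The literature review already reports no functional differences at three months and later. A null result on early recovery could then be taken as more evidence that the approaches do not differ, when the trial had little chance of showing a difference of the size it names.

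**Working it through.** **Inputs from the Protocol.** Significance 5%, power 80%, effect size 0.3, target difference 1000 steps per day, 55–60 per arm (ANALYSIS); 1:1 allocation and 100–120 in total (Study Design).

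**Assumptions.** The effect size is a standardised mean difference d, the natural reading for a t-test on mean steps. The test is two-sided, and all patients are analysed.

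**1. Attempt to reproduce 55–60 per arm.** By the normal approximation:

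n per arm = 2(z₀.₉₇₅ + z₀.₈₀)² / d² = 2(1.960 + 0.842)² / 0.3² = 174.4, so 175.

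The exact noncentral-t calculation gives 175.4, so 176 per arm and 352 in total. A one-sided test at 5% gives 138.1, so 139 per arm. The stated figure is not reproduced: 176/60 = 2.9 and 176/55 = 3.2.

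**2. Power and detectable effect at the planned sizes** (noncentral t; two-sided except the third column). The last two columns use SD = 1000/d and difference = d × 3333.

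| n per arm | Power at d = 0.3 | One-sided power at d = 0.3 | Detectable d at 80% power | SD at which that d is 1000 steps | Detectable steps if SD = 3333 |
|---|---|---|---|---|---|
| 50 | 31.8% | 43.8% | 0.566 | 1767 | about 1890 |
| 55 | 34.5% | 46.8% | 0.539 | 1855 | about 1800 |
| 60 | 37.1% | 49.6% | 0.516 | 1939 | about 1720 |

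As a check by the normal approximation at 55 per arm: 0.3 × √(55/2) − 1.960 = 1.573 − 1.960 = −0.387, and Φ(−0.387) = 34.9%.

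**3. The same sentence in steps.** If 1000 steps is 0.3 SD, then SD = 1000/0.3 = 3333 steps per day. If 55–60 per arm gives 80% power for 1000 steps, then SD = 1855–1939. Both cannot hold.

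**4. Other readings of 0.3** (two-sided 5%, 80% power).

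- Cohen's f = 0.3 with two groups is d = 0.6: 44.6, so 45 per arm (90 in total).
- A paired or one-sample effect of 0.3: 89.1, so 90 in total.
- Chi-squared w = 0.3: 87.2, so 88 in total.
- Correlation r = 0.3: (2.802/0.3095)² + 3 = 84.9, so 85 in total.

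None gives 110–120 in total.

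**5. Baseline adjustment.** Adjusting for a baseline value multiplies the required n by 1 − ρ². To bring 175 down to 55–60, ρ must be √(1 − 55/175) = 0.83 to √(1 − 60/175) = 0.81. The Protocol states no such correlation, and the comparison it names for continuous data is a t-test.

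**6. Enrolment.** Two arms of 55 make 110. The recruitment range starts at 100.

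**The case against.** The strongest reply is that 34–37% is a conditional figure. The Protocol gives no SD, so the power for 1000 steps is unknown: with 55–60 per arm it is 93–95% if the SD is 1500, 55–58% if it is 2500 and 34–37% if it is 3333. If 0.3 is the mistaken entry, the trial may be adequately sized for 1000 steps. This stands as a limit on the conclusion. It does not rescue the sentence, because 0.3 would then be wrong.

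A second reply is that 0.3 may be Cohen's f, with losses added. From 45 per arm, 20% loss gives 45/0.80 = 56.25, so 57, and 25% loss gives 45/0.75 = 60. On that reading, power with 55–60 analysed per arm would be 88–90%. It explains the figure plausibly but does not reproduce it, since the Protocol states neither the f scale nor a loss rate.

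Two smaller points are also fair. The t-test appears in a general paragraph, so its link to the sample-size sentence is inferred, although no other test of a step-count difference is named. The enrolment mismatch affects only the lower limit and is minor by itself.

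**Conclusion.** The concern holds. On the natural reading (two independent groups, d = 0.3, two-sided 5%), the stated inputs require 176 per arm. At 55–60 per arm they give 34–37% power, and at the lowest planned enrolment of 50 per arm they give 32%. The power figures assume that every randomised patient contributes step data; any loss lowers them.

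The check does not show which of the effect size, the implied SD and the sample size is mistaken, because the Protocol gives no SD. It does show that 0.3, 1000 steps, 80% power and 55–60 per arm cannot all be true together. As this is the only power claim in the Protocol and it concerns the main primary outcome, it must be corrected.

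**What to change.** First, state the scale of the effect size and the between-patient SD of daily steps that the calculation relies on, with its source. The SD should not be obtained by working back from the chosen sample size. Then replace the sentence according to that SD:

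- If the SD is about 1850–1940 steps per day, drop 0.3 and write: *With 55–60 patients per arm, two-sided 5% significance and 80% power, the detectable difference is about 0.52–0.54 SD, which equals 1000 steps per day for an SD of about 1850–1940.*
- If 0.3 is kept as the effect of interest, state that power with 55–60 per arm is about 34–37%.
- For any other SD, give the detectable difference as 0.52–0.54 times that SD.

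Change the recruitment range in Study Design from 100–120 to at least 110–120 to match the per-arm figure. State that the power figures refer to patients with analysable step data, since 110–120 contains no allowance for loss.

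The cost is one reworded sentence, one aligned range and possibly a less favourable stated power. No patients are needed beyond the stated 55–60 per arm.
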